10.5.7.5. Holter Monitoring

Continuous Holter recording will be performed for subjects from 15 minutes pre-treatment through 8 hours post-treatment any time a subject transitions from 2 mg to 3 mg etrasimod and at all timepoints specified in [Appendix 1](#) and [Appendix 2](#). A subject will be discharged from the study site with the Holter monitor in place and continue to wear the Holter monitor until Hour 8 (\pm 15 minutes) post-treatment administration. Subjects will be instructed how to remove and store the Holter monitor, record the time the device is removed, and to return the device for analysis at the next in-person study visit. If the subject requires extended in-clinic cardiac monitoring \geq 8 hours, the Holter will be removed on-site at Hour 8 prior to discharge. Holter data will be captured on the device and sent to the Holter laboratory. The Holter laboratory will be responsible for central reading, analysis, and interpretation. Holter recording results may be made available to study sites.

Holter recording will principally be used for determination of HR and potential arrhythmias (eg, pauses, AV block). Point estimates will be obtained at specified times. The central Holter laboratory may determine additional parameters or perform additional analyses from digitized Holter monitor recordings including but not limited to those indicated by the initial analyses or safety events. Additional information is provided in the Holter manual.

10.5.7.6. Pulmonary Function Monitoring

Based on changes in pulmonary function observed with the use of S1P receptor modulators fingolimod and siponimod, approved for relapsing multiple sclerosis ([GILENYA 2010](#), [MAYZENT 2019](#)), pulmonary function will be assessed in this study at Screening, Week 12, Week 24, Week 52, and ET if applicable ([Appendix 1](#) and [Appendix 2](#)).

Subjects experiencing clinically significant dyspnea or other respiratory AEs may need to have additional PFT testing as clinically indicated. Severity of respiratory AEs should be categorized using the CTCAE scale described in [Appendix 4](#). Investigators should consider interruption of study drug when there is a clinically significant respiratory AE considered related to study drug that leads to limitations in instrumental or self-care activities of daily living. The decision to interrupt study drug should be discussed with the Medical Monitor. Subjects should be promptly referred to a pulmonologist for further evaluation and treatment. The pulmonologist should be provided with a standard referral letter explaining the reason for the referral along with information about the investigational drug. Clinically significant respiratory AEs should be followed until there is stability, improvement, or resolution.

Re-initiation of study drug can only be considered if the respiratory AE has improved, stabilized, and/or resolved, the individual risk-benefit is favorable (as determined by the Investigator, in agreement with the pulmonologist) and after discussion with the Medical Monitor.

10.5.7.7. Ophthalmic Symptom Monitoring

Based on reports of macular edema observed with the use of S1P receptor modulators fingolimod and siponimod, approved for relapsing multiple sclerosis ([GILENYA 2010](#), [MAYZENT 2019](#)), ophthalmic testing, including OCT, will be assessed in this study at Screening, Week 12, Week 24, Week 52, and ET if applicable ([Appendix 1](#) and [Appendix 2](#)).

Subjects experiencing unexpected ophthalmic symptoms, including blurred vision, decreased visual acuity, or other clinically significant ocular AEs, without a known/suspected etiology may need to have repeated ophthalmoscopy and OCT testing performed. If there is evidence of new onset macular edema considered related to study drug, then study drug should be interrupted as appropriate and the subject should be monitored closely with the appropriate diagnostic and clinical work-up.

Unscheduled ophthalmology visits in case of any visual complaint:

If, during the study, there are complaints of decreased vision or identification of worsening visual acuity (equal to or more than 2 lines on a standard eye chart using best corrected vision) then an unscheduled ophthalmic examination should be performed.

At an unscheduled ophthalmology visit, the eye examination will include

- Best corrected visual acuity measurement
- Ophthalmoscopy (may include contact lens biomicroscopy to examine the macula and optic disc)
- OCT for all subjects to investigate a suspected diagnosis of macular edema

Note: For both scheduled and unscheduled visits, in case of suspected macular edema based on the ophthalmoscopy or a relevant increase of central foveal thickness, then FA may be performed.

Subjects with a diagnosis of macular edema considered related to study drug during the study must interrupt the study drug. These subjects must be followed up monthly with ophthalmologic evaluations until such time as resolution is confirmed or no further improvement is expected by the ophthalmologist (based on a follow-up period of not less than 3 months). These evaluations will include repeated best-corrected visual acuity, fundus examination, and OCT. FA may also be performed at the discretion of the ophthalmologist. If the subject does not show definite signs of improvement on examination by specialist testing (eg, OCT, FA) after interruption of study drug, then therapy for macular edema in conjunction with an ophthalmologist experienced in the management of this condition should be initiated at the Investigator's discretion.

For subjects diagnosed with macular edema, copies of the colored OCT and FA images (if conducted) should be kept by the investigative site as source documents. These documents may need to be submitted for review by an independent panel.

10.5.8. Adverse Events

10.5.8.1. Definitions

10.5.8.1.1. Adverse Event

An AE is any untoward medical occurrence that does not necessarily have a causal relationship with this treatment. An AE can therefore be any unfavorable and unintended sign, symptom, or disease temporally associated with the use of a medicinal product, whether or not considered related to the medicinal product.

AEs can include, but are not limited to, any of the following:

- Unfavorable changes in general condition
- Subjective or objective signs/symptoms
- Concomitant disease or accidents
- Clinically relevant adverse changes in laboratory parameters over the course of the study
- Pre-existing conditions that worsen in severity, increase in frequency, or have new signs/symptoms

Information on the grading and management of laboratory abnormalities according to assessment severity is provided in [Appendix 4](#) and [Appendix 5](#), respectively.

10.5.8.1.2. Serious Adverse Event

An AE should be classified as an SAE if it meets 1 of the following criteria:

Fatal:	The AE resulted in death.
Life-threatening:	The AE placed the subject at immediate risk of death. This classification does not apply to an AE that hypothetically might cause death if it were more severe.
Hospitalization:	The AE required or prolonged an existing inpatient hospitalization. Hospitalizations for elective medical or surgical procedures or treatments planned before the signing of informed consent in the study or routine check-ups are not SAEs by this definition.
Disabling/ incapacitating:	The AE resulted in a persistent or significant incapacity or substantial disruption of the subject's ability to conduct normal life functions.
Congenital anomaly or birth defect:	An adverse outcome in a child or fetus of a subject exposed to the study drug before conception or during pregnancy.
Medically significant:	The AE did not meet any of the above criteria but could have jeopardized the subject and might have required medical or surgical intervention to prevent 1 of the outcomes listed above or involves suspected transmission via a medicinal product of an infectious agent.

Additionally, in this study, any diagnosis of PML will be considered an SAE.

10.5.8.1.3. Adverse Drug Reaction

An adverse drug reaction (ADR) in the pre-approval clinical experience with a new medicinal product or its new usages, particularly as the therapeutic dose(s) may not be established, is any noxious and unintended response to a medicinal product related to any dose. The phrase "responses to a medicinal product" means that a causal relationship between a medicinal product and an AE is at least a reasonable possibility (ie, the relationship cannot be ruled out).

10.5.8.1.4. Adverse Events of Special Interest

Based on the mechanism of action of etrasimod and prior experience with other agents acting via a similar mechanism, potential events of interest may be identified. In addition to appropriate reporting of these events as an AE or an SAE, supplementary detailed information may be collected.

10.5.8.1.5. Severity

The severity of each AE will be assessed at the onset by the Investigator. When recording the outcome of the AE, the maximum severity of the AE experienced will also be recorded. The severity of each AE will be graded according to the CTCAE:

- | | |
|----------|---|
| Grade 1: | Mild; asymptomatic or mild symptoms; clinical or diagnostic observations only; intervention not indicated. |
| Grade 2: | Moderate; minimal, local or noninvasive intervention indicated; limiting age-appropriate instrumental activities of daily living. |
| Grade 3: | Severe or medically significant but not immediately life-threatening; hospitalization or prolongation of hospitalization indicated; disabling, limiting self-care activities of daily life (eg, preparing meals, shopping for groceries or clothes, using the telephone, managing money). |
| Grade 4: | Life-threatening consequences, urgent intervention indicated. |
| Grade 5: | Death related to AE. |

Additional information on CTCAE grading of AEs is provided in [Appendix 4](#).

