11.9.1. Safety Endpoints

- Incidence and severity of AEs
- Incidence and severity of laboratory abnormalities and change from Baseline in laboratory values (to include hematology, serum chemistry, coagulation, and urinalysis)
- Incidence of clinically significant vital sign abnormalities and changes from Baseline (may include 4 hours postdose on Day 1 and Week 24)
- ECGs
- Holter Monitoring
- Physical examination findings

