APPENDIX 4: GRADING OF CLINICAL AND LABORATORY ADVERSE EVENTS

All clinical and clinically significant laboratory abnormalities will be graded according to the CTCAE Scale for Severity of Adverse Events and Laboratory Abnormalities.

Examples of CTCAE terms and grading are provided for clinical adverse events (AEs) in [Table 10](#) and for laboratory abnormalities in [Table 11](#).

Table 10: Example of CTCAE Terms and Grading for Clinical Adverse Events

Respiratory, thoracic and mediastinal disorders					
CTCAE Term	Grade 1	Grade 2	Grade 3	Grade 4	Grade 5
Cough	Mild symptoms; nonprescription intervention indicated	Moderate symptoms, medical intervention indicated; limiting instrumental ADL	Severe symptoms; limiting self-care ADL	-	-
Definition: A disorder characterized by sudden, often repetitive, spasmodic contraction of the thoracic cavity, resulting in violent release of air from the lungs and usually accompanied by a distinctive sound.					
Dyspnea	Shortness of breath with moderate exertion	Shortness of breath with minimal exertion; limiting instrumental ADL	Shortness of breath at rest; limiting self-care ADL	Life-threatening consequences; urgent intervention indicated	Death
Definition: A disorder characterized by an uncomfortable sensation of difficulty breathing.					
Wheezing	Detectable airway noise with minimal symptoms	Moderate symptoms; medical intervention indicated; limiting instrumental ADL	Severe respiratory symptoms limiting self-care ADL; oxygen therapy or hospitalization indicated	Life-threatening consequences; urgent intervention indicated	Death
Definition: A disorder characterized by a high-pitched, whistling sound during breathing. It results from the narrowing or obstruction of the respiratory airways.					
Dizziness	Mild unsteadiness or sensation of movement	Moderate unsteadiness or sensation of movement; limiting instrumental ADL	Severe unsteadiness or sensation of movement; limiting self-care ADL	-	-
Definition: A disorder characterized by a disturbing sensation of lightheadedness, unsteadiness, giddiness, spinning or rocking.					

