Frequency and percentage of subjects who experience TEAE will be summarized by SOC, PT, and maximum reported relationship (treatment-related or not treatment-related). A treatment-related AE is defined as any TEAE that is assessed by the Investigator as Related or Probably Related to study treatment. TEAE that is assessed as Unlikely Related or Not Related will be defined as not treatment-related. TEAE with an unknown relationship will be considered as treatment-related.

Frequency and percentage of subjects who experience TEAE will be summarized by SOC, PT, and maximum reported severity. The severity will be graded according to the CTCAE (Grade 1 - mild, Grade 2 - moderate, Grade 3 - severe, Grade 4 – life-threatening or Grade 5 - death). If a subject experience more than one TEAE within different severity categories within the same SOC/PT, only the worst case (maximum reported severity) will be reported. TEAE with an unknown severity will be considered as severe.

Frequency and percentage of subjects who experience serious TEAE will be summarized by SOC and PT within SOC.

Frequency and percentage of subjects who experience treatment emergent AESI will be summarized by AESI category and PT.

Frequency and percentage of subjects who experience non-serious TEAE will be summarized by SOC and PT for DB and OLE period separately.

Listings of all AEs, all AEs leading to death, all serious AEs, all TEAEs leading to study drug discontinuation, and all TEAEs leading to study discontinuation will be provided.

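### The examples printed under Grade 3 of the AE severity scale are, in ordinary meaning, instrumental activities, so Grades 2 and 3 overlap for AEs graded on functional limitation

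*Protocol*

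**What the plan says.** Protocol section 10.5.8.1.5 states that "The severity of each AE will be graded according to the CTCAE" and then prints five generic grades. The functional part of Grade 2 is "limiting age-appropriate instrumental activities of daily living", with no examples. The functional part of Grade 3 is "disabling, limiting self-care activities of daily life (eg, preparing meals, shopping for groceries or clothes, using the telephone, managing money".

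The section refers to Appendix 4 for more on grading. Table 10 there uses the same two categories in its term-specific rows. For dizziness, Grade 2 is "Moderate unsteadiness or sensation of movement; limiting instrumental ADL" and Grade 3 is "Severe unsteadiness or sensation of movement; limiting self-care ADL". For dyspnea, Grade 2 is "Shortness of breath with minimal exertion; limiting instrumental ADL". The cough, wheezing and blurred vision rows, and vital capacity in Table 11, follow the same pattern. Appendix 4 lists no activities for either category.

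The grade feeds the safety analysis. Protocol section 11.9.1 lists "Incidence and severity of AEs" first among the safety endpoints, and section 2 makes safety part of the primary objective. SAP section 11.1 says: "Frequency and percentage of subjects who experience TEAE will be summarized by SOC, PT, and maximum reported severity".

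**The concern.** The scale works only if an investigator can tell an instrumental limitation from a self-care limitation. The one list offered as a guide is attached to self-care. It consists of household and community tasks (cooking, shopping, telephone use, handling money), which ordinary usage calls instrumental. If these count as self-care, little recognisable is left for Grade 2 to describe.

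At stake is the moderate/severe boundary in the maximum-severity tables. A site that follows the printed examples can record Grade 3 where a site that follows the category names records Grade 2. Because the SAP counts each subject at the worst grade, one upgraded event is enough to move that subject into the severe row. The arms are small, so a few such subjects would be visible.

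**Working it through.** The plan states no figure on this point, so the main check is a comparison of the texts.

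| Source | Grade 2 | Grade 3 | Activities listed |
|---|---|---|---|
| Protocol 10.5.8.1.5, generic scale | instrumental | self-care | four, under Grade 3 only |
| Protocol Appendix 4, Table 10, dizziness | instrumental | self-care | none |
| Protocol Appendix 4, Table 10, dyspnea | minimal exertion; instrumental | at rest; self-care | none |

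1. The category split is the same everywhere. Protocol section 10.5.7.6 also names the two categories separately. The documents therefore treat them as distinct.
2. Neither document defines or lists instrumental activities, and nothing corrects the parenthesis. The supplied text names no CTCAE version.
3. Test case: a subject is breathless on minimal exertion, comfortable at rest, and for that reason unable to shop. The Table 10 dyspnea row gives Grade 2. The generic examples in 10.5.8.1.5 give Grade 3. The two texts disagree on the same event.
4. For dyspnea, the Table 10 row settles the matter through its exertion criterion. For a term with no row in Appendix 4, the generic text is the only grading wording that the protocol prints, and there the overlap is unresolved.

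**Size per subject.** The planned arm sizes come from Protocol section 11.2, both cohorts combined:

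- 3 mg: 24
- 2 mg: 24 + 6 = 30
- placebo: 12 + 12 = 24

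One subject moved from a maximum of Grade 2 to a maximum of Grade 3 changes the arm's rate of Grade 3 or higher by 1/n:

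- n = 24: 1/24 = 4.2 percentage points
- n = 30: 1/30 = 3.3 percentage points

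This holds only if the subject has no other AE of Grade 3 or higher. The documents give no expected AE rates and no indication of how many AEs would be graded on function alone, so no total can be derived.

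**The case against.** The best case against the point has five parts.

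- The scale gives Grade 2 a category, not these four tasks. Calling them instrumental relies on the ordinary meaning of the word. This is correct and limits the wording of the point. It does not remove the overlap, because the same ordinary meaning is all an investigator has.
- The instrument in force is the CTCAE, and the terms shown in Table 10 have their own criteria: breathlessness at rest, acuity limits for blurred vision, severe unsteadiness. Grade 3 in the generic scale also carries wording on medical significance and hospitalization. This stands, and it confines the exposure mainly to AEs without a row in Appendix 4 that are graded on function.
- Grading in the double-blind period is blinded and the wording is common to all arms, so the text itself favours no arm. This also stands. The problem is inconsistency between sites and possible overstatement of absolute severe-event rates.
- Other decisions are largely insulated. Seriousness (10.5.8.1.2) and the cardiac discontinuation criteria (Table 8) do not use the grade, and the respiratory interruption rule (10.5.7.6) names both categories. The AE management figure in Appendix 5 is redacted, so no effect through it can be claimed.
- The 1/n arithmetic is true of any misclassified subject and is not evidence that misgrading will occur. Agreed; it shows scale only.

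A reader might go further and infer that an excess of dizziness, dyspnea or visual symptoms on etrasimod would show up as an excess of severe events. The documents do not support this: those terms have their own rows in Table 10 and are the better protected ones.

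**Conclusion.** The point holds as an inconsistency in an operative grading rule. The Grade 3 examples in 10.5.8.1.5 describe activities that, in ordinary meaning, belong to the category assigned to Grade 2. The two grades therefore overlap for AEs graded on functional limitation, mainly those with no Appendix 4 row. Such AEs can be recorded as severe, and sites can differ.

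Each reclassified subject is worth about 4.2 points in the 3 mg or placebo arm and 3.3 points in the 2 mg arm, assuming planned enrolment, every enrolled subject dosed, and no other AE of Grade 3 or higher in that subject.

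A reader might infer that moderate AEs will be graded as severe, or that the severe-event rate is overstated by some stated amount. The documents establish only that upgrading is possible. Any total would rest on an assumed count of affected subjects. Efficacy analyses and power are untouched.

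**What to change.** In Protocol section 10.5.8.1.5, reconcile the scale with Appendix 4 and the CTCAE version in use. Move the parenthesis from Grade 3 to Grade 2, where it serves as the examples of instrumental activities, and state the version. Send sites a short clarification.

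Before the double-blind lock, ask sites, under blind, to confirm the grade of Grade 2 and Grade 3 AEs that may have been graded on functional limitation. Both grades should be included so that corrections can go in either direction.

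The cost is small. The text change goes to the IRB/IEC under Protocol section 12.2. The query needs some new information from sites, because the AE fields listed in section 10.5.8.2.2 record severity but not the basis for the grade. No additional subjects, visits or assessments are needed.

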10.5.8.1.6. Relationship

The Investigator is obligated to assess the relationship (causal relationship) between the study drug and each occurrence of each AE. The AE relationship (causal relationship) to study drug must be characterized as 1 of the following categories:

- | | |
|-------------------|---|
| Not Related: | The AE does not follow a reasonable temporal sequence from administration of the drug, does not abate upon discontinuation of the drug, does not follow a known or hypothesized cause-effect relationship, and (if applicable) does not reappear when the drug is reintroduced, furthermore, there may exist a clear alternative medical explanation (eg, underlying disease state) or association with study procedure or study conduct. |
| Unlikely Related: | The temporal association between the AE and the drug is such that the drug is not likely to have any reasonable association with the AE. |
| Probably Related: | The AE follows a reasonable temporal sequence from administration of the drug and cannot be reasonably explained by the known characteristics of the subject's clinical state, environmental, or toxic factors, or other modes of therapy administered to the subject. |

Related: The AE follows a reasonable temporal sequence from administration of the drug, abates upon discontinuation of the drug, follows a known or hypothesized cause-effect relationship, and (if appropriate) reappears when the drug is reintroduced.

The Investigator will use clinical judgment to determine the relationship (causal relationship). Alternative causes, such as underlying disease(s), concomitant therapy, and other risk factors, as well as the temporal relationship of the event to the study drug administration should be considered and investigated. The Investigator should consult the IB and the Product Information of marketed products within the drug class, when applicable. For each AE, the Investigator must document in the medical notes that he/she has reviewed the AE and has provided an assessment of causality. There may be situations in which an SAE has occurred, and the Investigator has minimal information to include in the initial report to the Sponsor; however, the Investigator should always make an initial assessment of causality for every event before the initial transmission of the SAE to the Sponsor. The Investigator may change his/her opinion of causality based on subsequent receipt of information and send an SAE follow-up report with the updated causality assessment. The causality assessment is one of the criteria used when determining regulatory reporting requirements.

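### The four-level causality scale has no clear place for most events with plausible timing and a competing explanation, so the treatment-related TEAE table can fall below the protocol's own drug-reaction threshold

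*Protocol*

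**What the plan says.** Protocol 10.5.8.1.6 says the causal relationship of each AE "must be characterized as 1 of the following categories". The four levels, and the part of each that matters here, are:

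- **Not Related** begins as follows: "The AE does not follow a reasonable temporal sequence from administration of the drug, does not abate upon discontinuation of the drug". Further conditions cover mechanism and rechallenge, and the definition allows that a clear alternative medical explanation may exist.
- **Unlikely Related** rests on timing alone: "The temporal association between the AE and the drug is such that the drug is not likely to have any reasonable association". Nothing else is in the definition.
- **Probably Related** has two parts: "The AE follows a reasonable temporal sequence from administration of the drug and cannot be reasonably explained by the known characteristics". The explanations to be excluded are the clinical condition, environmental or toxic exposure, and other treatment.
- **Related** needs reasonable timing, and the event "abates upon discontinuation of the drug, follows a known or hypothesized cause-effect relationship". Reappearance on rechallenge is added where appropriate.

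Protocol 10.5.8.1.3 sets a different test for an adverse drug reaction: a causal relationship "is at least a reasonable possibility (ie, the relationship cannot be ruled out").

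SAP 11.1 reduces the four levels to two. Related and Probably Related are treatment-related; "TEAE that is assessed as Unlikely Related or Not Related will be defined as not treatment-related". A TEAE whose relationship is unknown is counted as treatment-related.

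**The concern.** The drug-reaction definition asks whether a relationship can be excluded. The lowest level that the SAP counts as related asks whether every other reasonable explanation can be excluded. These are different thresholds, and the second is higher. Events with plausible timing and another possible cause lie between them. An infection during lymphocyte reduction, or dizziness on treatment, is an ordinary example in this trial.

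If these events are recorded as Unlikely Related, the by-arm treatment-related figures leave out events that the protocol itself would call possible drug reactions. Because no definition says where they belong, sites may also place the same kind of event differently. Safety is part of the primary objective, and the arms are small enough for a few subjects to move the figure visibly.

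**Working it through.** The plan gives no rate or count on this point, so there is no figure to reproduce. The check is to read the definitions against one type of event.

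**Step 1. Place the event.** Take an AE with plausible timing and a reasonable alternative explanation.

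| Level | Condition that decides | Met? |
|---|---|---|
| Not Related | No reasonable temporal sequence | No, timing is plausible |
| Unlikely Related | Timing makes an association unlikely | No, timing is plausible |
| Probably Related | No reasonable other explanation | No, there is one |
| Related | Abatement on discontinuation and a known or hypothesized mechanism | Only if both hold |

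Leaving rechallenge aside, abatement (yes/no) crossed with mechanism (yes/no) gives 2 × 2 = 4 combinations. One fits Related; 4 − 1 = 3 fit no level as worded. The three include every event for which drug was continued, because abatement on discontinuation was then never observed.

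**Step 2. Compare with the drug-reaction definition.** An association judged unlikely has not been ruled out. A mixed event can therefore meet 10.5.8.1.3 and still be rated Unlikely Related.

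**Step 3. Follow it into the SAP.** The SAP 11.1 split lies between Unlikely Related and Probably Related, so that event is tabulated as not treatment-related. The rule for unknown relationship does not catch it, because the forced choice has supplied an answer.

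**Step 4. Effect per subject.** Planned numbers from Protocol 11.2:

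- 3 mg: 24 (Cohort 2 only)
- 2 mg: 24 + 6 = 30
- Placebo: 12 + 12 = 24

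A subject whose only potentially related TEAE is a mixed event rated Unlikely Related lowers the subject-level treatment-related rate by 1/24 = 4.2 points (3 mg or placebo) or 1/30 = 3.3 points (2 mg). A subject with another TEAE already rated related does not change that overall rate, because the summary uses the maximum reported relationship.

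**Step 5. Check the obvious remedy.** If a fifth, possibly-related level were added and applied from Cohort 2 onward, it would cover 24/24 = 100% of the planned 3 mg arm, 12/24 = 50% of placebo and 6/30 = 20% of 2 mg. Ascertainment would then differ by dose.

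**The case against.** Several counter-arguments have force.

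- **The scale is not wholly without a place.** Related does not exclude an alternative explanation, and the protocol gives a hypothesized mechanism for both infection and dizziness. Such events can be Related if they abate on discontinuation. This stands, and it narrows the gap to the remaining combinations.
- **Nothing sends mixed events to Unlikely Related.** The protocol relies on clinical judgment and asks the Investigator to weigh alternative causes as well as timing. This also stands. The misplacement is possible, not prescribed. Judgment still has no defined level in which to put the answer.
- **The treatment-related table is not the main safety evidence.** The safety endpoint is the incidence and severity of AEs, and TEAEs, serious TEAEs and AEs of special interest are summarized whatever their relationship. In a blinded, placebo-controlled comparison those tables carry the inference. The SAP also never equates treatment-related with the ADR definition. This limits the point to the relationship-based output.
- **No between-arm bias is shown.** Ratings are made blind, so misplacement can occur in every arm.

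A reader might infer that expedited reporting of serious unexpected reactions fails, because "The causality assessment is one of the criteria used when determining regulatory reporting requirements". The documents do not support that. Protocol 10.5.8.3.1 sends every SAE to the Sponsor within 24 hours whatever its relationship. Section 10.5.8.3.2 ties expedited reporting to the ADR concept, not to the four-level rating. No section excludes an SAE rated Unlikely Related.

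**Conclusion.** The point holds as a mismatch between three sections. Protocol 10.5.8.1.3 sets a threshold that the scale in 10.5.8.1.6 does not contain, and the SAP 11.1 split lies above it. The treatment-related TEAE table can therefore understate events that meet the protocol's own definition of a drug reaction.

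The size is known only per subject: 4.2 points for 3 mg or placebo and 3.3 points for 2 mg. This assumes the planned arm sizes, and that the subject has no other TEAE counted as related. A reader might want to turn this into a total for each arm, but the documents give no AE rates, so any number of affected subjects would be a guess. The all-causality safety tables are unaffected. This is an inexpensive improvement to one set of tables, not a flaw in the safety evaluation.

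**What to change.** Keep the four-level scale, so that causality is ascertained in the same way in both cohorts and hence across doses. In SAP 11.1, add to the relationship tables (14.3.1.4.1, 14.3.1.4.2 and 14.3.1.4.3) a supportive row counting, by arm, subjects with any TEAE not rated Not Related. Events of unknown relationship stay in both rows.

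Add a footnote saying that the main row is a lower bound and the supportive row an upper bound for events whose relationship was not ruled out, given the ratings recorded. A mixed event that a site rated Not Related would remain outside both rows.

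The cost is one extra row and a less favourable related-event figure. No new data, eCRF change or re-rating is needed.
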